**REGULATORY FRAMEWORK:**

Please indicate all that apply:

	DOD (Department of Defense)
	DOE (Department of Energy)
	DOJ (Department of Justice)
	ED (Department of Education)
	EPA (Environmental Protection Agency)
	FDA (Food and Drug Administration)
	HHS (Department of Health and Human Services)
	VA
	Other:

Is this a clinical trial under ICH-GCP E6?  Yes  No

If yes, please confirm that the research team is familiar with and agrees to comply with the investigator requirements cited in ICH-GCP E6.  Yes  No

ICH-GCP E6 can be accessed by copying and pasting this URL into your browser:  
<http://www.fda.gov/downloads/Drugs/Guidances/ucm073122.pdf>

**FUNDING:**

Click ERA record: FP00006210, FP00008226 (Continuation)

## 1. Objectives

- 1.1. We propose a non-inferiority randomized controlled trial (RCT) with a primary outcome of lactation continuation through 8 weeks postpartum comparing women receiving immediate (first 24 hours postpartum) versus standard (4-6 weeks postpartum) etonogestrel (ENG) implant insertion. Secondary outcomes include: number of days of postpartum bleeding, time to resumption of sexual activity, postpartum sexual function (measured by Female Sexual Function Index (FSFI) score), and postpartum mood as measured by Edinburgh Postnatal Depression Scale (EPDS) score. We will also measure breastfeeding exclusivity, factors effecting discontinuation of breastfeeding, timing of breast feeding discontinuation, satisfaction with postpartum contraceptive counseling, satisfaction with the contraceptive implant and satisfaction with bleeding pattern in the immediate and standard groups.
- 1.2. The contribution of the proposed research is to determine if immediate ENG implant insertion (within 24 hours) is non-inferior to standard insertion (4-6 weeks) postpartum. We hypothesize that inserting the ENG implant in the first 24 hours postpartum is not inferior to standard insertion at 4-6 week postpartum for breastfeeding continuation through 8 weeks postpartum.
  - 1.2.1. Primary Objective 1: To compare continuation of lactation through eight weeks postpartum between women in the immediate versus standard group. Our hypothesis is that breastfeeding continuation at eight weeks postpartum is not inferior in women in the immediate insertion group of the ENG implant than in those with standard insertion. Our study is powered for this outcome.
- 1.3. Secondary Objectives: To compare number of days of postpartum bleeding, postpartum sexual function as measured by FSFI score, and postpartum mood as measured by EPDS score, time to resumption of sexual activity, exclusive breastfeeding method, factors associated with discontinuing breastfeeding, timing of breastfeeding discontinuation, patient satisfaction with postpartum contraception counseling and the implant and patient satisfaction with bleeding pattern between the immediate and standard insertion groups.
  - 1.3.1. Secondary Objective 1: To compare the total number of days of postpartum bleeding in the immediate versus standard group at 2, 4, and 8 weeks postpartum . Our hypothesis is that number of days of bleeding in the immediate insertion group is not significantly different than the number of days of bleeding in the standard insertion group.
  - 1.3.2. Secondary Objective 2: To compare postpartum sexual function as measured by Female Sexual Function Index (FSFI) score at 4, 8, and 12 weeks postpartum. Our hypothesis is that FSFI scores for the immediate insertion group are not significantly different than FSFI scores for the standard insertion group.

PROTOCOL TITLE: Effect of immediate versus standard postpartum insertion of the contraceptive implant on breastfeeding outcomes

- 1.3.3. Secondary Objective 3: To compare postpartum mood as measured by EPDS score at 2, 4, and 8 weeks postpartum. Our hypothesis is that EPDS scores for the immediate insertion group are not significantly different than EPDS scores for the standard insertion group.
- 1.3.4. Secondary Objectives 4: To compare exclusive breastfeeding through 6 months postpartum between the immediate versus the standard group.
- 1.3.5. Secondary Objective 5: To compare postpartum factors associated with discontinuing breastfeeding between the immediate versus the standard group.
- 1.3.6. Secondary Objective 6: To compare timing of breastfeeding discontinuation through 6 months postpartum between the immediate versus the standard group.
- 1.3.7. Secondary Objective 7: To compare participant satisfaction with postpartum contraception counseling in women enrolled in the study and in those women who opted not to enroll in the study.
- 1.3.8. Secondary Objective 8: To compare participant satisfaction with timing of ENG implant insertion between the immediate versus the standard group.

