**Regarding secondary objectives:**

1. Bleeding patterns: Irregular bleeding is the most common side effect noted by users of the ENG contraceptive implant. Limited evidence shows that this holds true in the postpartum period (17). In a retrospective cohort study of women who underwent immediate versus standard postpartum insertion of the implant, approximately one in five women requested discontinuation of use due to irregular bleeding, and this rate was not significantly different between the two groups (17). Evidence on the effect of immediate postpartum insertion of the ENG contraceptive implant on lochia is limited and mixed. An RCT of immediate versus standard postpartum insertion of the six-rod levonorgestrel implant showed significantly more total days of bleeding for the immediate insertion group (18), while a more recent Australian prospective cohort study demonstrated no lengthening of the duration of lochia (postpartum bleeding) with immediate insertion (19). We will measure postpartum bleeding patterns using periodic review of a patient bleeding diary that quantifies bleeding on a daily basis as “none”, “spotting”, “bleeding” or “heavy bleeding”. As patient dissatisfaction with irregular bleeding likely mediates discontinuation for this reason, we will also measure patient satisfaction with their bleeding pattern postpartum.

PROTOCOL TITLE: Effect of immediate versus standard postpartum insertion of the contraceptive implant on breastfeeding outcomes

2. Postpartum mood changes: It is possible that postpartum use of an ENG implant may affect postpartum mood. In a retrospective study of adverse event reporting for ENG implant use, it was noted that postpartum depression was a commonly reported adverse event, and therefore may be associated with implant use in the postpartum period (20). In addition, in a secondary analysis study, use of the ENG implant in the postpartum period was associated with a higher risk of later antidepressant use compared to women with no hormonal contraceptive use (21). Women's perception of contraceptives' effect on their mood is a significant factor in contraception discontinuation (22). We hypothesize that timing of implant insertion will not increase postpartum depression related mood changes as measured by the EPDS. We will also assess patient perception of impact of ENG implant insertion on mood.

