3. Postpartum sexual function: Effect of postpartum ENG implant use on postpartum sexual function is not well studied. However, in a 2016 study of impact of LARC use on sexual function (not in the postpartum period), it was noted that there was no objective change in sexual function with initiation of copper IUD, levonorgestrel IUDs or ENG implant (24). We hypothesize that this is also true in the postpartum period and that the effect of timing of ENG implant insertion will not affect postpartum sexual function as measured by the FSFI. The FSFI is a validated tool for assessing female sexual function that been used in the aforementioned studies, both in assessing LARC effects and in the postpartum period (25). Patient perceptions of the effect of their contraceptive on sexual experience may affect contraceptive continuation rates regardless of objective findings on sexual function. In a 2018 study of the impact of sexual function and perceived effect of contraceptive method on sexual experience on continuation rates of multiple LARCs, patients' perception of a negative impact of the contraceptive on sex life was the strongest predictor of discontinuation (26). We will assess patient centered perception of impact of ENG implant insertion on sexual function.
4. Postpartum exclusive breastfeeding through 6 months postpartum: Receiving only breast milk is known as exclusive breastfeeding (EBF). AAP and WHO promote EBF for the first six month of life of infants because it provides multiple health benefits to babies and to the mother (1,5). Nationally, 46.9 % and 24.9% of women exclusively breastfeed at 3 and 6 months, respectively; in New Mexico 53.0% and 27.6% breastfeed exclusively at 3 and 6 months, respectively (6). Since this data does not provide information about the mothers who use contraception and how many of the exclusively breastfeed, we will assess this information.

**PROTOCOL TITLE:** Effect of immediate versus standard postpartum insertion of the contraceptive implant on breastfeeding outcomes

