## 13.Data Analysis

13.1 We will conduct a primary analysis per protocol and a secondary analysis per intention to treat. The rationale behind this strategy is to analyze both approaches and examine the result for consistency. A Repeated measures ANOVA analysis will be used for continuation of breastfeeding. To evaluate secondary outcomes between the two

**PROTOCOL TITLE:** Effect of immediate versus standard postpartum insertion of the contraceptive implant on breastfeeding outcomes

groups we will use the T-test, Wilcoxon Rank Sum test, Chi-squared test, or Fisher's exact test as appropriate. Secondary outcomes to be evaluated are to compare time of exclusivity of breastfeeding, mix breastfeeding, factors associated with discontinuing breasts feeding, time of breastfeeding discontinuation and patient satisfaction with postpartum contraception counseling and with timing of placing the implant between both groups. If there are significant differences between treatment groups, multivariable linear (for continuous outcomes) and logistic (for dichotomous outcomes) regression will be utilized in addition to control for confounding.

13.2 This study is a non-inferiority trial designed to demonstrate that immediate postpartum insertion of the ENG implant is non-inferior to standard ENG implant insertion with respect to the proportion of women who fail to breastfeed by 8 weeks after delivery. The failure rate for continuation of breastfeeding under the current treatment, standard insertion, is expected to be 30%.

The following sample size determination and plan for data analysis was developed in conjunction the University of New Mexico Clinical and Translational Science Center (CTSC). The non-inferiority margin for both primary outcomes is 15%, meaning that immediate insertion can be regarded as non-inferior (in terms of breastfeeding continuation) to standard insertion if the difference in rate with immediate insertion is no more than 15% worse than with standard insertion. To achieve 80% power with a 1-sided Type 1 error of 5% utilizing the Z test (unpooled) 62 participants are required in each group for a total 124. Accounting for the expected loss of follow up of 20%, the total subjects 149, round to 150. We intend to enroll up to 200 participants due to unanticipated loss to follow up, so this should ensure that we have enough data for data analysis.

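### The bleeding, sexual function and mood hypotheses would be met by a non-significant difference test, with no margin, interval criterion or power behind them

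*Combined protocol and SAP*

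**What the plan says.** Section 1.3 of the combined protocol and SAP sets out three comparisons, each followed by a hypothesis:

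- **1.3.1, bleeding days at 2, 4 and 8 weeks:** "number of days of bleeding in the immediate insertion group is not significantly different than the number of days of bleeding" in the standard group.
- **1.3.2, FSFI at 4, 8 and 12 weeks:** "FSFI scores for the immediate insertion group are not significantly different than FSFI scores for the standard insertion group".
- **1.3.3, EPDS at 2, 4 and 8 weeks:** "EPDS scores for the immediate insertion group are not significantly different than EPDS scores for the standard insertion group".

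The Background (the part of section 2.3 on secondary objectives, items 2 and 3) restates two of these as predictions about the effect itself. For mood, it expects that "timing of implant insertion will not increase postpartum depression related mood changes as measured by the EPDS". For sexual function, it expects that "timing of ENG implant insertion will not affect postpartum sexual function as measured by the FSFI".

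For secondary outcomes, section 13.1 says "we will use the T-test, Wilcoxon Rank Sum test, Chi-squared test, or Fisher's exact test as appropriate". The list of outcomes that follows covers breastfeeding measures and satisfaction, and does not name bleeding days, FSFI or EPDS. Sections 1.1 and 7.1 do define these three as secondary, and no other method is given for them.

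The only margin (15%, section 13.2) and the only power statements (1.2.1, 5.3 and 13.2) concern breastfeeding continuation.

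**The concern.** Failing to reject a null hypothesis of no difference does not show that there is no difference. When the hypothesis is itself worded as the absence of significance, a smaller or noisier trial is more likely to confirm it. The plan avoids this for breastfeeding continuation, where it sets a margin and a one-sided error rate, but does not carry that reasoning over to these three outcomes.

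The plan's own background makes harm plausible. It cites a randomised trial of a different contraceptive implant with more bleeding days after immediate insertion, and reports linking the etonogestrel implant to postpartum depression and later antidepressant use. It says that perceived mood effects are a significant factor in contraceptive discontinuation, and that about one in five women in a cohort asked to stop because of irregular bleeding. The results are meant to inform counselling, where a statement of no difference and a statement that differences of about a third of an SD are not excluded carry different messages.

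**Working it through.** **Plan's own figure.** There is no sample size or power for bleeding days, FSFI or EPDS to reproduce. The only sample size, 62 evaluable per group, is for the primary outcome. With 30% discontinuation in both groups, a 15-point margin, one-sided 5% and 80% power, the unpooled formula gives n = (0.21 + 0.21) × (1.645 + 0.842)² / 0.15² = 115.4, so 116 per group. The stated 62 is obtained if true discontinuation in the immediate group is taken as 25%, which the plan does not state. That is a separate question; here 62 is used only as a documented group size.

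**Inputs from the documents (sections 5.3 and 13.2).** 62 evaluable per group; a goal of 75 per group; up to 200 enrolled, which is 100 per group at 1:1 with no loss.

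**Assumptions.** Two-sided 5% (no level is stated for secondary outcomes), two-sample t-test, one visit at a time, differences d in SD units. The documents give no SD or important difference for these measures, so a range of d is shown.

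**Step 1: chance of a non-significant result when a true difference d exists.** This is 1 − power, with power from the non-central t distribution with 2n − 2 degrees of freedom and non-centrality d × √(n/2). For d = 0.30 and n = 62, the non-centrality is 0.30 × √31 = 1.67 against a critical value of 1.98.

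| n per group | d = 0.30 | d = 0.40 | d = 0.50 |
|---|---|---|---|
| 62 | 62% | 40% | 21% |
| 75 | 55% | 32% | 14% |
| 100 | 44% | 20% | 6% |

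**Step 2: 95% confidence interval half-width,** t(0.975; 2n − 2) × √(2/n):

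- n = 62: 1.980 × 0.1796 = 0.36 SD
- n = 75: 1.976 × 0.1633 = 0.32 SD
- n = 100: 1.972 × 0.1414 = 0.28 SD

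The half-width is also close to the true difference at which power is 50%. A non-significant result is therefore the more likely outcome only for true differences below about 0.36, 0.32 or 0.28 SD respectively.

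**Step 3: what a margin would require.** For non-inferiority at one-sided 2.5%, 80% power and no true difference, n = 2 × ((1.960 + 0.842)/margin)². A margin of 0.3 SD needs 175 per group and 0.5 SD needs 63. At 62 per group the trial could support only a wide margin, of about 0.5 SD.

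**The case against.** A reader might infer that the plan contains a rule under which p>0.05 will be reported as proof of no harm. The documents do not support that. The sentences in 1.3.1 to 1.3.3 and in the Background are predictions, each objective opens neutrally as a comparison, and no analysis text says how a non-significant result will be reported. Nothing prevents the investigators from giving intervals. This part of the objection stands: the wording invites the misreading but does not prescribe it.

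A reader might also infer that non-significance is likely whatever the true difference. It is not: at 0.50 SD the test would usually detect the difference at every documented group size. The documents do not show that 0.30 SD is an important difference on any of these scales, and the figures are for a t-test, whereas 13.1 also allows the Wilcoxon test, which may suit bleeding days better.

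The omission of the three outcomes from the list in 13.1 leaves some doubt about which test applies. The general sentence on secondary outcomes most naturally covers them, and the plan offers no alternative, so the doubt is a further reason to clarify 13.1.

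Finally, section 1.2.1 claims power only for breastfeeding continuation, and the plan also collects satisfaction with bleeding and perceived effects on mood and sexual function. These points lessen the weight of the three tests, but do not tell a reader how to interpret a non-significant one.

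**Conclusion.** The point holds as a gap in how three secondary hypotheses are framed and judged. As written, a non-significant difference test would satisfy each of them, and nothing in the plan separates that result from evidence of no effect. At the documented group sizes, a true 0.30 SD difference would go undetected in 44% to 62% of trials, and a 0.50 SD difference in 6% to 21%. These figures rest on the assumed two-sided 5% t-test and on effects in SD units; whether 0.30 SD matters clinically cannot be settled from the documents. The finding does not depend on the exact group size or on the primary sample-size calculation. Because the outcomes are secondary and no decision rule hangs on them, the consequence is a possible overstated conclusion about bleeding, sexual function or mood. The primary result is not at risk from this.

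**What to change.** - Reword 1.3.1 to 1.3.3 as estimation objectives: to estimate the between-arm difference in bleeding days, FSFI and EPDS. Bring the matching sentences in the Background into line.
- Name the three outcomes in 13.1 and state the analysis for each.
- Report the between-arm difference with its 95% confidence interval at each planned visit: weeks 2, 4 and 8 for bleeding days and EPDS; weeks 4, 8 and 12 for FSFI.
- State in 13.1 that p>0.05 will not be read as no difference, and that conclusions will name the largest difference the interval does not exclude.

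No new margin, data or participants are needed, and the intervals can be computed from the data already planned. The downside is a more cautious conclusion on these secondary outcomes. The primary analysis does not change.

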## 7. Study Endpoints

	Screen -ing	First 24 hours Post partu m	1-7 days*	2 weeks	4 weeks	6 weeks	8 weeks	12 weeks	24 weeks END	Up to 1 year pp	Up to 5 years pp
Intake	X										
Postpartum contraception counseling satisfaction survey	X				X						
Device Insert		X			X	X					
Exclusive breastfeeding			X	X	X		X	X	X		
Breastfeeding discontinuation				X	X		X	X	X		
Retrospective Breastfeeding Discontinuation Chart Review Form										X	
Contraceptive use			X		X		X	X	X		X
Diary collection				X	X		X				
Mood (EPDS)				X	X		X				
Sexual function (FSFI)					X		X	X			
Bleeding log review				X	X		X				

7.1. The primary endpoint of this research are to compare continuation of lactation at eight week postpartum between women in the immediate with standard group.

The secondary endpoints of this research are to compare number of days of postpartum bleeding, postpartum sexual function as measured by FSFI score, and postpartum mood as measured by EPDS score, time to resumption of sexual activity, exclusive breastfeeding method, factors associated with discontinuing breastfeeding, timing of breastfeeding discontinuation, patient satisfaction with postpartum contraception counseling and the implant and patient satisfaction with bleeding pattern between the immediate and standard insertion groups.

As in other studies of breastfeeding and hormonal contraception, we will continue to follow women out to 6 months. A survival analysis will be performed to determine longer-term effect of hormonal contraception on breastfeeding.

**PROTOCOL TITLE:** Effect of immediate versus standard postpartum insertion of the contraceptive implant on breastfeeding outcomes

- 7.2. The primary study endpoint is also a safety endpoint: breastfeeding continuation through 8 weeks. We have developed a Data Safety and Monitoring Plan related to these endpoints (please see below).
- 7.3. No exploratory endpoints will be conducted in this research.

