The questionnaires will contain data about breastfeeding, postpartum depression, and sexual function. A paper diary will be provided to aid the participant in daily recording of data. We will also include a retrospective data collection instrument to account for those we miss at the primary data collection points for breastfeeding information. If the primary questions have been answered either prospectively or retrospectively, then they get the normal prospective survey. If participants do not meet this criteria or if they miss a previous survey, then they will receive a retrospective survey. The diary will be collected at 2, 4, and 8 weeks. If possible, 2-3 good phone numbers will be obtained as well as addresses for each participant. Participants will have a phone number to contact study personnel at their specified site during standard work hours: Monday-Friday 8am- 4:30 pm with any concerns or adverse events. If they call after-hours, a voicemail system will be available, and the participant will be contacted the next working day.

*Data collection instruments*

Data collection instrument	Manner of collection	Timing	Included data
Enrollment form	Medical chart review  In-person, telephone and/or online via UNM's REDCap	After delivery  At enrollment	Participant & neonate medical history, delivery details  contraceptive history, contraceptive bridge-methods, lactation history, lactation and work expectations
Contraceptive Counseling Survey	In-person, telephone and/or online via UNM's REDCap	At enrollment and 4 weeks postpartum	Satisfaction with contraceptive counseling
Breastfeeding Survey	In-person, telephone and/or online via UNM's REDCap	2, 4, 8, 12, 24 weeks postpartum	Breastfeeding continuation, exclusivity, reasons for discontinuation if applicable, infant weight, resumption of intercourse, and satisfaction with contraception
EPDS	In-person, telephone and/or online via UNM's REDCap	2, 4, 8 weeks postpartum	Postpartum depression scale
FSFI	In-person, telephone and/or online via UNM's REDCap	4, 8, 12 weeks postpartum	Sexual function scale

PROTOCOL TITLE: Effect of immediate versus standard postpartum insertion of the contraceptive implant on breastfeeding outcomes

Bleeding diary	Paper or UNM's REDCap	Reviewed at 2, 4, 8 weeks. Collected at 2, 4, and 8 weeks	Bleeding patterns Side effects

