## **25. Consent Process**

25.1.1. The inclusion and exclusion criteria for study participation will be reviewed by a member of the research team to confirm eligibility. Prior to consent, the study will be described verbally to women, and potential subjects will receive a copy of the consent form to read. If patients are comfortable enrolling in the study at that point, they may do so. All potential participants will be reassured that declining study participation will have no effect on the care that they receive. If patients choose not to participate, they will not be approached again unless they broach the subject. Women who elect to participate will be informed about the standard risks, benefits and alternatives of the procedure per standard of care. Co-investigators or trained research staff will follow HRPO regulations for written documentation of consent or verbal consent. For women ages 13-17, we will obtain parental consent which could also occur verbally by phone and collected via mail or e-mail. Electronic consent will be noted on the updated consent form. Due to the pandemic, research coordinators are mainly working from home and going through the consent with participants by phone for the safety of everyone. Privacy is still maintained as the coordinator ensures they have a place they can talk privately by phone.

25.1.2. The consent discussion will take approximately 5-10 minutes after the consent has been read by the potential participant. Research staff will review the consent with the potential participant and provide ample opportunity for the subject to ask questions in a private setting.

25.1.3 Steps that will be taken to minimize the possibility of coercion or undue influence include providing ample opportunity for the subject to ask questions they may have about research, providing time for the possible participants to think about participating in the study and providing privacy for subjects.

25.1.4 Research staff will confirm the participant's interest and allow more opportunity for questions before the consent form is finally signed or electronically signed by the patient.

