**Partial Waiver of HIPAA Authorization for Screening/Recruitment**

*Complete the following additional questions/attestations if the records you will review to identify potential subjects and/or determine eligibility include Protected Health Information (PHI).*

6. Will you be recording any PHI when conducting the records review to identify potential subjects and/or determine eligibility?

Yes. Describe: *We will only record the reason the patient was not eligible and their name in order to avoid reviewing a patient's information more than once.*

No

7. If you answered “Yes” to question 6 above, please describe when you will destroy identifiers (must be the earliest opportunity consistent with the conduct of the research) or provide justification for why they must be retained:

*We will destroy identifiers once the study is complete and closed with the IRB.*

8. The PHI accessed or recorded for identification/screening purposes will not be reused or disclosed to (shared with) any other person or entity, except as required by law, for authorized oversight of the research study, or for other research for which the use or disclosure of the PHI would be permitted under the Privacy Rule.

True

False

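### Secondary Objective 7 compares enrolled women with women who declined, but the rest of the plan compares the two arms and describes no data from decliners

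*Combined protocol and SAP*

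**What the plan says.** Section 1.3.7 sets Secondary Objective 7 as a comparison of satisfaction with postpartum contraception counselling "in women enrolled in the study and in those women who opted not to enroll in the study".

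Four other places give the same outcome a different contrast. Section 1.1 lists "satisfaction with postpartum contraceptive counseling, satisfaction with the contraceptive implant and satisfaction with bleeding pattern in the immediate and standard groups". Section 7.1 names as a secondary endpoint "patient satisfaction with postpartum contraception counseling and the implant and patient satisfaction with bleeding pattern between the immediate and standard insertion groups", and Section 1.3 uses the same words. Section 13.1, which assigns the tests, refers to "patient satisfaction with postpartum contraception counseling and with timing of placing the implant between both groups".

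On collection, the instrument table in Section 12 times the Contraceptive Counseling Survey "At enrollment and 4 weeks postpartum". The schedule in Section 7 has a row, "Postpartum contraception counseling satisfaction survey", marked under Screening and at 4 weeks. On women who decline, Section 25.1.1 states: "If patients choose not to participate, they will not be approached again unless they broach the subject".

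**The concern.** The two definitions are different questions. Enrolled women versus decliners is an observational contrast between people who chose differently. Immediate versus standard is a randomised contrast among people who all agreed to take part. They need different data, different populations and different analyses, and neither can stand in for the other.

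Two things are at stake. First, an analyst following the procedures as described would reach the end of the trial with no described comparison group for Objective 7. Second, because the plan holds two definitions of one outcome, a reader cannot tell which was pre-specified, and the choice could be made after the data are seen.

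**Working it through.** No figure in the plan bears on this point: no sample size, effect size or power is given for Objective 7. The check is to set the sections side by side.

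**Step 1. Which groups are compared?**

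| Section | Contrast for counselling satisfaction |
|---|---|
| 1.3.7 | Enrolled versus declined |
| 1.1 | Immediate and standard arms |
| 1.3 | Immediate versus standard |
| 7.1 | Immediate versus standard |
| 13.1 | The two groups, in a paragraph about treatment groups |

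One section against four. The rationale for this outcome (Section 2.3, item 6 of the secondary objectives) speaks of surveying how women perceived their counselling and names no decliner group.

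**Step 2. Is there a described source of decliner data?** A decliner comparison needs a survey occasion, a number of women and an analysis.

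- *Occasion.* The instrument table gives enrolment and 4 weeks. A woman who declines has no enrolment, and the rule in 25.1.1 against approaching her again leaves no 4-week contact.
- *Number.* Section 5 counts only enrolled women: a ceiling of 200 and a target of 75 per arm.
- *Analysis.* Section 13.1 contains no comparison of enrolled women with decliners and no method for a non-randomised contrast.

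None of the three is described.

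**Step 3. If the arm comparison is the intended one, which survey can carry it?** Section 20.1 says most women will enrol antenatally. Section 12 randomises those women, and women enrolled on labour and delivery before labour, shortly after admission for the birth; women enrolled postpartum are randomised after consent. The enrolment survey therefore normally comes before allocation. A score measured before allocation has the same expected distribution in both arms, so an arm comparison of enrolment scores alone could show only chance differences. The 4-week survey is the one that can carry an arm effect, with the enrolment score as a baseline. Section 13.1 does not say which time point is used.

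**Step 4. What would a 4-week difference mean?** Section 12 books standard insertion at 4 weeks, with two further weeks for rescheduling. Some women in the standard arm may answer the 4-week survey before, or close to, insertion. A difference between arms could then partly express satisfaction with timing, which is Secondary Objective 8.

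**The case against.** The strongest reply is that the Section 7 schedule marks the survey under Screening, in the same column as Intake. Read generously, every woman approached could complete the survey before deciding, which would supply a group of decliners. The rule in 25.1.1 follows a reassurance that declining does not affect care, so it reads as a bar on repeated solicitation. It does not forbid a survey completed in the same encounter in which the woman says no.

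Part of this stands. A reader might infer that no decliner will contribute any data, but the documents do not establish that; they establish only that no such collection is described. The Screening mark is at most an ambiguous hint: the instrument table says enrolment, and the hint cannot extend to the 4-week survey or supply the missing analysis.

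A reader might also infer that decliners could not be surveyed because no consent route exists. That goes too far. The consent form was not available for this check, and Section 25.1.1 allows verbal consent. The partial waiver in the checklist concerns review of medical records, so it neither permits nor prohibits a survey. Its statement "We will only record the reason the patient was not eligible and their name" is about ineligible women, not eligible women who declined.

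Finally, counselling about the implant largely takes place before randomisation and is not what is randomised. An arm comparison of counselling satisfaction is therefore a limited question even when correctly timed. That is a reason to interpret it cautiously, not a reason to leave two definitions in place.

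**Conclusion.** The point holds as an internal inconsistency. Section 1.3.7 conflicts with 1.1, 1.3, 7.1 and 13.1, and the comparison it names cannot be answered from the data the protocol describes.

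Its size is small. It touches one of eight numbered secondary objectives, which carries no stated hypothesis and no power calculation. A reader might take it as a sign that the trial cannot answer its main question; the documents do not support that, because the primary comparison of breastfeeding at 8 weeks uses neither the survey nor the decliners. It is an improvement worth making, not a condition for the trial's validity.

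The conclusion assumes that the instrument table, rather than the Screening mark, governs when the survey is given. The remark about enrolment scores assumes that the survey is completed before the woman knows her allocation. That is clear for women enrolled before labour. For women enrolled postpartum, consent and randomisation fall close together, and the order of survey and allocation is not stated.

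**What to change.** Reconcile 1.3.7 with 1.3, 7.1 and 13.1. Suggested text for 1.3.7: *To compare satisfaction with postpartum contraception counselling at 4 weeks postpartum between the immediate and standard insertion groups.*

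Add to 13.1: *Counselling satisfaction will be compared between groups using the 4-week survey, adjusted for the enrolment survey completed before randomisation. A difference may partly reflect satisfaction with the timing of insertion (Secondary Objective 8) and will be interpreted together with that outcome.*

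The schedule and the instrument table should use the same term for the first survey, and should say that it is completed before allocation is disclosed.

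The cost is about one sentence in each of 1.3.7 and 13.1, plus a table label. No new data are needed. The adjustment is a real change to 13.1, which at present plans simple two-group tests and brings in regression only if the groups differ.

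The downside is losing the comparison with women who declined. If the sponsor wants to keep it, the alternative is to describe the decliner survey in full: when it is given, under what consent or waiver, to how many women, and with what non-randomised analysis. Sections 1.3, 7.1 and 13.1 would then have to list it as a separate outcome.
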